#### 2.2.3.2. Plasma Pharmacokinetics of PF-06741086

### 2.2.3.2.1. Following Administration of Single IV or SC Doses in B7841001

A summary of PK parameters following single dose SC administration of PF-06741086 at 30, 100, and 300 mg and single dose IV infusion over 1 hour at 150 and 440 mg is presented in Table 1.

Peak plasma concentration (Cmax) was reached at 1 hour, ie, first sample collection at the end of infusion, following IV administration and 48 to 108 hours following SC administration. Under the same dosing route, exposures (particularly area under the curve (AUC)) appeared to increase greater than proportionally with dose, which suggests that PF06741086 may undergo target mediated drug disposition. As dose increases, mean terminal half-life (t½) of PF-06741086 increased from 33.3 h (100 mg SC) to 79.5 h (440 mg IV) in non--Japanese participants. Mean values of Cmax and area under the concentration time curve from time 0 to the time of the last quantifiable concentration (AUClast) were similar between the White participants and Japanese participants following PF-06741086 300 mg SC dosing indicating no apparent difference in PK based on observed data. Mean AUCinf was moderately higher in Japanese participants due to one out of 2 Japanese participant reporting a t½ of 122 hours and as a result of which, the extrapolated AUCinf of the Japanese participant was outside the range observed in the non--Japanese participants.

### 2.2.3.3. Pharmacodynamics of PF-06741086

### 2.2.3.3.1. Following Administration of Single IV or SC Doses in B7841001

Pharmacologic effects reflective of coagulation pathway activation, which includes dPT, prothrombin fragment 1+2 (PF1+2), D-dimer, as well as the TGA parameters of lag time and peak thrombin generation, were monitored in Study B7841001. Total plasma TFPI level was also measured to reflect target binding.

Preliminary PD data following single dose SC administration of PF06741086 at 30, 100, and 300 mg and single dose IV infusion over 1 hour at 150 and 440 mg suggested that treatment related changes were observed for all PD endpoints and generally the response was exposure dependent. Pharmacologic effects on total TFPI as well as a number of PD biomarkers (eg, PF1+2, TGA lag time and thrombin generation, and D-dimer) persist >7 days following administration a single 300 mg SC dose of PF06741086. To support the planned weekly dosing following SC administration, area under the effect curve for change from baseline values (ie, 0H on Day 1) from Days 17 for each PD endpoint was calculated. While changes were observed at all dose levels for some PD endpoints (eg, TGA lag time and TGA thrombin generation), others were only observed at a higher dose level (eg, D-dimer, PF1+2 and dPT at 100 mg and above, and total TFPI at 150 mg and above). Maximum or near maximum effect occurred most frequently following a single dose of 300 mg SC based on these AUC values.

[figure not shown]
# 2.2.3.3.2. Following Administration of Multiple SC Doses in B7841002

Treatment related changes were observed for all PD endpoints in	all dose col	norts as e	expected.
CCI			
	e were no		_
suggesting that these PD changes were reflective of excessive p	harmacolog	y. PD r	esponses
were mostly consistent between inhibitor and non-inhibitor	r participar	nts and	between
hemophilia A and B participants.			

#### 2.3. Benefit/Risk Assessment

The nonclinical and clinical safety profile of PF-06741086 has been adequately characterized to support evaluation of the current clinical study in the Chinese hemophilia population. Participation in this study may benefit future patients with hemophilia.

#### **Potential Benefits**

Additionally, weekly SC dosing

with PF-06741086 may substantially reduce the burden of care associated with prophylactic treatment, eliminating the need for frequent IV infusions, potentially obviating the need for indwelling central venous catheters, and reducing or eliminating acute treatment of bleeding episodes with FVIII or FIX (or bypass agents), thereby reducing the antigenic exposure to FVIII

PF-06741086 B7841010 Final Protocol Amendment 1 22-Oct-2020

or FIX.

#### **Potential Risks**

Individuals may experience risks or discomforts at the anatomical site of SC injection with PF-06741086. Injection Site Reactions, which may include pain, swelling, bruising, induration, and hematoma, are considered adverse drug reactions for PF-06741086.

Potential risks for treatment with PF-06741086 are thrombi or emboli. Depending on location and severity, thrombi or emboli may be life threatening or fatal.

Because PF-06741086 is a fully human IgG1 with no endogenous counterpart, the anti-drug antibody response (ADA) is expected to primarily affect the PK, efficacy and/or measurement of PF-06741086. An additional potential immunogenicity risk is the ADA-induced hypersensitivity. Therefore, individuals with a diagnosis or history of thrombotic or ischemic disease (including myocardial infarction, deep venous thrombosis or pulmonary embolism), individuals with coronary artery disease and individuals with an allergy to hamster protein should be excluded from study participation.

More detailed information about the known and expected benefits and risks and reasonably expected adverse events (AEs) of PF-06741086 may be found in the investigator's brochure (IB), which is the single reference safety document (SRSD) for this study.

# 3. OBJECTIVES AND ENDPOINTS

Ob	jectives	Endpoints
Pri	mary:	Primary:
	To determine the safety and tolerability of a single SC dose of PF-06741086 administered to Chinese adult participants with severe hemophilia A or B with or without inhibitors.	• Frequency, severity and causal relationship of treatment emergent adverse events (TEAEs) and withdrawals due to TEAE; Day 1 up to Day 42.
		• Frequency and magnitude of abnormal laboratory findings (including hematology, PT/INR, APTT, chemistry, urinalysis, fibrinogen, ATIII activity and cardiac troponin I); Day 1 up to Day 28.
		Changes from baseline in vital signs (blood pressure, pulse rate, temperature and respiration rate) measurements 12-lead electrocardiogram (ECG) parameters and physical examination; Day 1 up to Day 28.
		• Frequency, severity and causal relationship of injection site reactions; Day 1 up to Day 7.
Sec	condary:	Secondary:
•	To characterize the PK profile of a SC single dose of PF-06741086.	
 
Plasma PF-06741086 concentrations as determined by a validated assay Day 1 up to Day 28, and noncompartmental PK parameters including Cmax, Tmax, AUClast, AUCinf, terminal half-life, Vz/F, CL/F.
 

•	To characterize the PD profile of a SC single dose of PF-06741086.	• TFPI (total and free); Thrombin generation (including lag time, peak thrombin generation and endogenous thrombin generation potential); Prothrombin fragment 1+2 (PF 1+2); D-dimer; Dilute prothrombin time (dPT); Day 1 up to Day 28.
•	To characterize the immunogenicity of a single SC dose of PF-06741086.	Frequency of anti-drug antibody (ADA) and neutralizing antibody (NAb) production against PF-06741086; Day 1 up to Day 28. Only positive ADA samples and the corresponding baseline sample will be tested in the NAb assay.

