- a. The full physical examination (PE) planned for Screening may be performed on Day -1 before dosing at the discretion of the Investigator. If a full PE is done at Screening visit, then a brief PE is to be conducted on Day-1. After Day -1, brief examinations based on signs and symptoms will be performed if clinically indicated at the discretion of the Investigator to assess changes from baseline/previous visits of any ongoing symptoms.
- b. Vital signs to be assessed include pulse rate, respiration rate, temperature, and supine blood pressure.
- c. Differential hematology panel required at Screening, Day 1, and Day 7. Differential is optional at additional timepoints, as clinically indicated.
- d. Participants must be fasting for 12 hours prior to blood draw.
- e. A single sample to measure FVIII or FIX activity is to be collected after minimum washout period completed for prescribed factor-replacement product: FVIII replacement therapy for at least 72 hours; Extended half-life FVIII replacement therapy for at least 4× half-life; FIX replacement therapy for at least 4× half-life; bypass agent therapy from rFVIIa, prothrombin complex concentrate (PCC) or activated prothrombin complex concentrate (aPCC) for at least 72 hours.
- CD4 cell count test if HIV positive.
- g. Triplicate ECGs will be obtained at baseline pre-dose on Day 1. Single ECGs will be required at all additional timepoints unless ECG or troponin I is abnormal, in which case a triplicate ECG is required.
- PD blood sample including assessments for: Tissue factor pathway inhibitor (TFPI) (total and free), Thrombin Generation Assay (TGA), Prothrombin fragment 1+2 (PF1+2),
   D-dimer, Dilute prothrombin time (dPT).
- i. Participants with positive ADA results may be requested to return for additional follow-up visits after final planned follow-up visit.
- j. The follow-up Visit at Day 42 could be a Phone Follow-Up visit or a face to face clinic visit at the discretion of the investigator.
- k. Assessments for study early discontinuation or termination refer to Day7 visit. To note that cTnI should be assessed if discontinuation/termination occurs prior to Day 4. ADA and NAb sample will be also collected in case of study early discontinuation or termination.

PF-06741086 B7841010 Final Protocol Amendment 1 22-Oct-2020

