#### 4.2. Scientific Rationale for Study Design

Study B7841010 will be conducted in Chinese adult participants 18 to <75 years of age with severe hemophilia A or B, with or without inhibitor. This population also matches the entry criteria for the global pivotal Phase 3 study. The mechanism of action of PF-06741086 through the extrinsic cascade predicts it would be effective in both forms of hemophilia. Similarly, it is acceptable to enroll both those with inhibitors and those without, because the mechanism of action is not expected to be influenced by the presence of inhibitors to either FVIII or FIX. The clinical risk/benefit profile for this population is considered appropriate for the evaluation of PK, PD, safety and tolerability of PF-06741086.

The primary objective of Study B7841010 is to evaluate the safety and tolerability of a single SC dose of PF-06741086. Secondary objectives include evaluating the PK, PD properties and immunogenicity of PF-06741086. Selection of the PD endpoints and sampling schedule are based on results from non-clinical studies, the Phase 1 FIH study and Phase 1b/2 first-in patient (FIP) study results. They will reflect either target binding by PF-06741086 (ie, TFPI [total and free] levels) or downstream pharmacologic effects of TFPI inhibition (ie, dPT, TGA, PF1+2 and D-dimer). Thrombosis is a potential risk for inhibition of TFPI, and PF-06741086 is expected to significantly inhibit TFPI, particularly at the highest dose levels. To minimize this risk, hemophilia patients with a known history of thrombotic, ischemic or coronary artery disease, or known pro-thrombotic conditions (eg, Protein C deficiency) will be excluded from this study. Safety monitoring will include laboratory parameters that may be modulated due to coagulopathy (eg, [PT]/INR, APTT, fibrinogen, ATIII and platelet counts) and parameters to screen for possible thrombotic events (eg, cardiac troponin I). Laboratory endpoints to detect excessive modulation of the coagulation pathway will be monitored during the period of peak drug exposure, until at least 28 days have passed since the investigational drug administration.

Potential risks for treatment with PF-06741086 are thrombi or emboli. Depending on location and severity, thrombi or emboli may be life threatening or fatal. An additional potential risk for treatment with PF-06741086 is ADA-induced hypersensitivity. Additional safety information for PF-06741086 is available in the IB.

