3. ENDPOINTS AND BASELINE VARIABLES: DEFINITIONS AND CONVENTIONS

3.1. Primary Endpoints

- Frequency, severity and causal relationship of TEAEs and withdrawals due to TEAE; Day 1 up to Day 42.
- Frequency and magnitude of abnormal laboratory findings (including hematology, PT/INR, APTT, chemistry, urinalysis, fibrinogen, ATIII activity and cTnI); Day 1 up to Day 28.
- Changes from baseline in vital signs (blood pressure, pulse rate, temperature and respiration rate) measurements, 12-lead ECG parameters and physical examination; Day 1 up to Day 28.
- Frequency, severity and causal relationship of injection site reactions; Day 1 up to Day 7.

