6. ANALYSES AND SUMMARIES

6.1. Primary Endpoints (Safety Analyses)

All safety analyses will be performed on the safety population (as defined in Section 4).

Analysis of frequency, severity and causal relationship of AEs, TEAEs from Day 1 up to Day 42, and injection site reactions from Day 1 up to Day 7 will be provided. Changes from baseline in vital sign (blood pressure (BP), pulse rate, temperature and respiration rate) measurements and ECG parameters from Day 1 up to Day 28 will be summarized. Physical examination findings from Day 1 up to Day 28 will be listed. Frequency and magnitude of abnormal laboratory findings (including hematology, PT/INR, APTT, chemistry, urinalysis, fibrinogen, ATIII activity, and cTnI), ECG, BP, and pulse rate abnormalities from Day 1 up to Day 28 of potential clinical concern will be described. Safety data will be presented in tabular and/or graphical format and summarized descriptively, where appropriate, according to sponsor reporting standards.

For ECG data, the number of participants with uncorrected QT values >500 msec will be summarized. Listings of subjects with any single postdose value ≥500 msec will also be produced for QTcF. Numbers and percentages of subjects meeting the categorical criteria will be provided. All planned and unplanned measurements will be counted in these categorical summaries. All values meeting the criteria of potential clinical concern will be listed.

Seperate analysis for PT/INR, APTT, fibrinogen, ATIII activity and cTnI will include:

- Descriptive summary including n, mean, median, standard deviation, geometric mean, geometric coefficient of variation (geocv%), minimum, and maximum, will be reported from Day 1 up to Day 28.
- Listing of abnormalities.

Analysis change from baseline for PT/INR, APTT, fibrinogen, ATIII activity and cTnI will include:

• Descriptive summary including n, mean, median, standard deviation, minimum, and maximum, will be reported from Day 1 up to Day 28.

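### The primary laboratory endpoint states a Day 1 to Day 28 window for eight components, but four of them have no scheduled sample after Day 7 (after 72 h for cardiac troponin I)

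*Protocol*

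**What the plan says.** Protocol 1.1 and 3 give one window for the whole laboratory endpoint. In section 3 it reads "abnormal laboratory findings (including hematology, PT/INR, APTT, chemistry, urinalysis, fibrinogen, ATIII activity and cardiac troponin I); Day 1 up to Day 28". SAP 2.1 and 3.1 carry it over; in 3.1 it is "Frequency and magnitude of abnormal laboratory findings (including hematology, PT/INR, APTT, chemistry, urinalysis, fibrinogen, ATIII activity and cTnI); Day 1 up to Day 28".

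SAP 6.1 builds analyses on the same window. It describes abnormal laboratory findings of potential clinical concern over that period. It then adds: "Seperate analysis for PT/INR, APTT, fibrinogen, ATIII activity and cTnI will include" a descriptive summary and a listing of abnormalities, followed by a change-from-baseline summary for the same five items. Both summaries carry the period "minimum, and maximum, will be reported from Day 1 up to Day 28".

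The timing of each test is set by the Schedule of Activities (Protocol 1.3). Table 3 (Protocol section 8) gives the number of blood draws in the study period and in follow-up.

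Two further pairs of statements concern timing:

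- **cTnI at early withdrawal.** SoA footnote k asks for cTnI if the participant leaves before Day 4. Section 7.2 asks for it if withdrawal comes before discharge from the research unit, or Day 7.
- **Last safety contact.** The SoA places it at Day 42 with a window of 7 days either side. Section 8.3.1 requires active adverse event collection for at least 42 calendar days after the last dose.

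**The concern.** This is a primary endpoint, in a study whose named potential risks are thrombi and emboli (Protocol 2.3 and 4.2). A frequency needs a period over which abnormalities were looked for. If results for platelets, liver tests or troponin appear under a Day 1 to Day 28 label, a reader will take the absence of late abnormalities as something observed in every participant. For most of that period no sample is planned, so the absence would mostly mean that nobody was scheduled to look.

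The two further pairs matter for a similar reason. Sites could follow either cTnI rule and be compliant with one section but not the other. The last planned contact can also fall before the stated minimum collection period is over.

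**Working it through.** No power or sample-size calculation applies: the study is descriptive, with six participants. The check compares the stated window with what is scheduled.

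**Step 1. Last scheduled sample per component (SoA rows).** Dosing is on Day 1, so Day 28 is nominally 27 days post-dose, Day 7 is 6 days and Day 4 is 3 days (72 h).

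| Component | Scheduled post-dose samples | Last | Short of Day 28 |
|---|---|---|---|
| Hematology | 24 h, Day 7 | Day 7 | 21 days |
| Chemistry | 24 h, Day 7 | Day 7 | 21 days |
| Urinalysis | 24 h, Day 7 | Day 7 | 21 days |
| cTnI | 24 h, 72 h | Day 4 | 24 days |
| PT/INR, APTT, fibrinogen, ATIII | 24 h, Days 7, 14, 21, 28 | Day 28 | 0 |

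The stated window is met by 4 of 8 components.

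**Step 2. Cross-check with Table 3 (study period + follow-up draws).** Hematology 3 + 0, chemistry 3 + 0, cTnI 3 + 0, coagulation panel 3 + 3. One study-period draw is pre-dose, so the post-dose counts are 2, 2, 2 and 5, as in the SoA. Table 3 covers blood only and has no urinalysis row; for urinalysis the evidence is the SoA alone. Footnote c, "Differential hematology panel required at Screening, Day 1, and Day 7", concerns only the differential, so the hematology point also rests on the SoA row and Table 3.

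**Step 3. Size of the uncovered period.**

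- Hematology, chemistry, urinalysis: (27 − 6)/27 = 21/27 = 78%.
- cTnI: (27 − 3)/27 = 24/27 = 89%.
- Scheduled post-dose samples over six participants: 2 × 6 = 12 for each of these four, against 5 × 6 = 30 for each coagulation test.

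**Step 4. Other sources of later values.** Protocol 8.2.4 has clinically significant abnormal results repeated. Appendix 2 allows unscheduled tests for perceived safety concerns. Footnote k and section 7.2 prescribe hematology, chemistry and urinalysis at an early-discontinuation visit, whenever that falls and without a safety trigger. For cTnI, that visit adds a value only before Day 4 or before Day 7, depending on which rule is used. None of these sources samples every participant at planned times after Day 7.

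**Step 5. The two further pairs.**

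- The cTnI rules give different answers for a withdrawal on Days 4 to 6. In practice this is mainly Days 5 and 6, because Day 4 already has a scheduled cTnI draw.
- Day 42 ± 7 is Day 35 to Day 49, or 34 to 48 days post-dose. The last scheduled contact can come 42 − 34 = 8 days before the minimum in 8.3.1. At the nominal Day 42 it is 41 days post-dose, 1 day short.

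**The case against.** **The window is only an outer limit.** The wording can be read as a ceiling for a pooled category, with the timing of each test left to the SoA. Protocol 8.2.4, Protocol Appendix 2 and SAP 3.5.2 all defer in that way, so no site would be unsure what to draw. That part stands: conduct is not affected. As an account of the endpoint it does not hold. Every other window in the same table matches its last scheduled assessment: TEAEs Day 42; vital signs, ECG and physical examination Day 28; injection site reactions Day 7; PK, PD and immunogenicity Day 28. The injection site entry shows that the table shortens a window when collection stops at Day 7.

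**Little depends on it.** With six participants, no hypotheses and descriptive summaries only, no inference is invalidated. This stands and keeps the point modest. Individual participants are also protected by repeat and unscheduled tests, confinement to Day 7 and ECGs to Day 28.

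**Stronger readings that the documents do not support.**

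- A reader might infer that the SAP 6.1 cTnI summary cannot be produced. It can, from the pre-dose, 24 h and 72 h draws; it simply has no scheduled data after 72 h.
- A reader might infer that all later values would be triggered by a safety concern. Early-discontinuation visits are not.
- A reader might infer that section 4.2 makes a broken promise: "Laboratory endpoints to detect excessive modulation of the coagulation pathway will be monitored during the period of peak drug exposure, until at least 28 days". The sentence names neither the endpoints nor the peak period. If it means the safety tests named just before it ("Safety monitoring will include laboratory parameters that may be modulated due to coagulopathy (eg, [PT]/INR, APTT, fibrinogen, ATIII and platelet counts"), none is scheduled between 24 h and Day 7. If it means the PD markers, which section 2.2.3.3.1 introduces with "Pharmacologic effects reflective of coagulation pathway activation, which includes dPT, prothrombin fragment 1+2 (PF1+2), D-dimer", they are drawn at 24, 48 and 72 h and on Days 7 to 28. The 48 to 108 h peak-time range in section 2.2.3.2.1 is given for SC dosing as a whole in healthy participants, and the value for 300 mg alone cannot be read from the text. This is at most a request to say which endpoints are meant.

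**Conclusion.** The mismatch is real and is one of definition and reporting. The stated Day 1 to Day 28 window is supported by scheduled sampling for PT/INR, APTT, fibrinogen and ATIII. It is not supported for hematology, chemistry and urinalysis (scheduled to Day 7) or for cTnI (scheduled to 72 h). For these four, a frequency to Day 28 is not systematically ascertained, with 78% or 89% of the window lacking a planned sample.

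The percentages assume nominal visit days and count scheduled samples only. The conclusion does not depend on how many unscheduled tests occur, since those are not systematic. It says nothing about whether the schedule itself is clinically adequate.

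The cTnI withdrawal rules and the Day 42 contact against the 42-day minimum are smaller, separate contradictions. The 8-day figure is the earliest permitted visit. Section 8.3.1 still obliges collection for the full period, but no scheduled contact secures it when the visit is early.

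**What to change.** State the laboratory window per analyte in Protocol 1.1 and 3 and in SAP 2.1, 3.1 and 6.1, as the SoA now collects it:

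- hematology, chemistry and urinalysis: to Day 7;
- cTnI: to Day 4 (72 h);
- PT/INR, APTT, fibrinogen and ATIII: to the Day 28 visit.

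Label tables and listings the same way, and identify values from repeat, unscheduled or early-discontinuation tests as such. If the sponsor would rather keep the Day 28 window, the endpoint and the SoA must be reconciled some other way; the choice of schedule is the sponsor's.

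In the same revision, reconcile footnote k with section 7.2 on cTnI, and the Day 42 contact window with section 8.3.1.

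The wording route adds no procedures and no blood. It gives a narrower stated window. Because it touches a primary endpoint definition, Protocol section 9 would call for a protocol amendment alongside the SAP edit if the change is judged major.
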